10.3.1. Definition of AE

AE Definition

 • An AE is any untoward medical occurrence in a participant administered a pharmaceutical product and which does not necessarily have a causal relationship with the study intervention. An AE can therefore be any unfavorable and unintended sign (including an abnormal laboratory finding), symptom, or disease (new or exacerbated) temporally associated with the use of a medicinal (investigational) product, whether or not related to the medicinal (investigational) product. • An AE is any untoward medical occurrence, unintended disease or injury, or untoward clinical signs (including abnormal laboratory finding) in study participants, users, or other persons, whether or not related to the investigational medical device. This definition includes events related to the investigational medical device or comparator and events related to the procedures involved except for events in users or other persons, which only include events related to investigational devices.

Events Meeting the AE Definition

 • Any abnormal laboratory test results (hematology, clinical chemistry, or urinalysis) or other safety assessments (for example, electrocardiogram, radiological scans, vital signs measurements), including those that worsen from baseline, considered clinically significant in the medical and scientific judgment of the investigator (that is, not related to progression of underlying disease). • Exacerbation of a chronic or intermittent preexisting condition including either an increase in frequency and/or intensity of the condition. • New condition detected or diagnosed after study intervention administration even though it may have been present before the start of the study. • Signs, symptoms, or the clinical sequelae of a suspected drug-drug interaction. • Signs, symptoms, or the clinical sequelae of a suspected overdose of either study intervention or a concomitant medication. Overdose per se will not be reported as an

AE/SAE unless it is an intentional overdose taken with possible suicidal/self-harming intent. Such overdoses should be reported regardless of sequelae.

- Lack of efficacy or failure of expected pharmacological action per se will not be reported as an AE or SAE. Such instances will be captured in the efficacy assessments. However, the signs, symptoms, and/or clinical sequelae resulting from lack of efficacy will be reported as AE or SAE if they fulfill the definition of an AE or SAE.

Events NOT Meeting the AE Definition

 • Any clinically significant abnormal laboratory findings or other abnormal safety assessments that are associated with the underlying disease, unless judged by the investigator to be more severe than expected for the participant’s condition. • The disease/disorder being studied or expected progression, signs, or symptoms of the disease/disorder being studied, unless more severe than expected for the participant’s condition. • Medical or surgical procedure (for example, endoscopy, appendectomy): the condition that leads to the procedure is the AE. • Situations in which an untoward medical occurrence did not occur (social and/or convenience admission to a hospital). • Anticipated day-to-day fluctuations of preexisting disease(s) or condition(s) present or detected at the start of the study that do not worsen.

10.3.2. Definition of SAE

An SAE is defined as any untoward medical occurrence that, at any dose, meets one or more of the criteria listed:

a. Results in death

b. Is life-threatening
 
The term life-threatening in the definition of serious refers to an event in which the participant was at risk of death at the time of the event. It does not refer to an event, which hypothetically might have caused death, if it were more severe.

c. Requires inpatient hospitalization or prolongation of existing hospitalization
 
 • In general, hospitalization signifies that the participant has been admitted to hospital or emergency ward (usually involving at least an overnight stay) for observation and/or treatment that would not have been appropriate in the physician’s office or outpatient setting. Complications that occur during hospitalization are AEs. If a complication prolongs hospitalization or fulfills any other serious criteria, the event is serious. When in doubt as to whether hospitalization occurred or was necessary, the AE should be considered serious.

 • Hospitalization for elective treatment of a preexisting condition that did not worsen from baseline is not considered an AE.

d. Results in persistent disability/incapacity
 
 • The term disability means a substantial disruption of a person’s ability to conduct normal life functions. • This definition is not intended to include experiences of relatively minor medical significance such as uncomplicated headache, nausea, vomiting, diarrhea, influenza, and accidental trauma (for example, sprained ankle) which may interfere with or prevent everyday life functions but do not constitute a substantial disruption.

e. Is a congenital anomaly/birth defect
 
 • Abnormal pregnancy outcomes (for example, spontaneous abortion, fetal death, stillbirth, congenital anomalies, ectopic pregnancy) are considered SAEs.

f. Other situations:
 
 • Medical or scientific judgment should be exercised by the investigator in deciding whether SAE reporting is appropriate in other situations such as important medical events that may not be immediately life-threatening or result in death or hospitalization but may jeopardize the participant or may require medical or surgical intervention to prevent one of the other outcomes listed in the above definition. These events should usually be considered serious. • Examples of such events include invasive or malignant cancers, intensive treatment in an emergency room or at home for allergic bronchospasm, blood dyscrasias or convulsions that do not result in hospitalization, or development of drug dependency or drug abuse.

g. Resulted in medical or surgical intervention to prevent life-threatening illness or injury or permanent impairment to a body structure or a body function.

10.3.3. Definition of Product Complaints

Product Complaint

A PC is any written, electronic, or oral communication that alleges deficiencies related to the identity, quality, durability, reliability, safety, effectiveness, or performance of a study intervention. When the ability to use the study intervention safely is impacted, the following are also PCs:
 
 ○ Deficiencies in labeling information, and ○ Use errors for device or drug-device combination products due to ergonomic design elements of the product.

- PCs related to study interventions used in clinical trials are collected in order to ensure the safety of participants, monitor quality, and to facilitate process and product improvements.
- Investigators will instruct participants to contact the site as soon as possible if he or she has a PC or problem with the study intervention so that the situation can be assessed.
- An event may meet the definition of both a PC and an AE/SAE. In such cases, it should be reported as both a PC and as an AE/SAE.

10.3.4. Recording and Follow-Up of AE and/or SAE and Product Complaints

AE, SAE, and Product Complaint Recording

- When an AE/SAE/PC occurs, it is the responsibility of the investigator to review all documentation (for example, hospital progress notes, laboratory reports, and diagnostics reports) related to the event.
 - The investigator will then record all relevant AE/SAE/PC information in the participant's medical records, in accordance with the investigator's normal clinical practice. AE/SAE information is reported on the appropriate CRF page and PC information is reported on the Product Complaint Form.
- NOTE: An event may meet the definition of both a PC and an AE/SAE. In such cases, it should be reported as both a PC and as an AE/SAE.
- It is **not** acceptable for the investigator to send photocopies of the participant's medical records to Sponsor or designee in lieu of completion of the CRF page for AE/SAE and the Product Complaint Form for PCs.
 - There may be instances when copies of medical records for certain cases are requested by Sponsor or designee. In this case, all participant identifiers, with the exception of the participant number, will be redacted on the copies of the medical records before submission to Sponsor or designee.
 - The investigator will attempt to establish a diagnosis of the event based on signs, symptoms, and/or other clinical information. Whenever possible, the diagnosis (not the individual signs/symptoms) will be documented as the AE/SAE.

Assessment of Intensity

The investigator will make an assessment of intensity for each AE and SAE reported during the study and assign it to one of the following categories:

- Mild: A type of adverse event that is usually transient and may require only minimal treatment or therapeutic intervention. The event does not generally interfere with usual activities of daily living.
- Moderate: A type of adverse event that is usually alleviated with additional specific therapeutic intervention. The event interferes with usual activities of daily living, causing discomfort but poses no significant or permanent risk of harm to the research participant.
- Severe: A type of adverse event that interrupts usual activities of daily living, or significantly affects clinical status, or may require intensive therapeutic intervention. An AE that is assessed as severe should not be confused with a SAE. Severe is a category utilized for rating the intensity of an event; and both AEs and SAEs can be assessed as severe.

An event is defined as “serious” when it meets at least one of the pre-defined outcomes as described in the definition of an SAE, NOT when it is rated as severe.

Assessment of Causality

- The investigator is obligated to assess the relationship between study intervention and each occurrence of each AE/SAE. The investigator will use clinical judgment to determine the relationship/
- A “reasonable possibility” of a relationship conveys that there are facts, evidence, and/or arguments to suggest a causal relationship, rather than a relationship cannot be ruled out.
- Alternative causes, such as underlying disease(s), concomitant therapy, and other risk factors, as well as the temporal relationship of the event to study intervention administration will be considered and investigated.
- The investigator will also consult the IB in their assessment.
- For each AE/SAE, the investigator **must** document in the medical notes that he/she has reviewed the AE/SAE and has provided an assessment of causality.
- There may be situations in which an SAE has occurred, and the investigator has minimal information to include in the initial report to Sponsor or designee. However, it is very important that the investigator always make an assessment of causality for every event before the initial transmission of the SAE data to Sponsor or designee.
- The investigator may change their opinion of causality in light of follow-up information and send a SAE follow-up report with the updated causality assessment.
- The causality assessment is one of the criteria used when determining regulatory reporting requirements.

Follow-up of AEs and SAEs

 • The investigator is obligated to perform or arrange for the conduct of supplemental measurements and/or evaluations as medically indicated or as requested by Sponsor or designee to elucidate the nature and/or causality of the AE or SAE as fully as possible. This may include additional laboratory tests or investigations, histopathological examinations, or consultation with other health care professionals. • If a participant dies during participation in the study or during a recognized follow-up period, the investigator will provide Sponsor or designee with a copy of any post-mortem findings including histopathology.

10.3.5. Reporting of SAEs

SAE Reporting via Paper Form

 • Facsimile transmission of the SAE paper form is the preferred method to transmit this information to the medical monitor or the SAE coordinator. • Initial notification via telephone does not replace the need for the investigator to complete and sign the SAE CRF pages within the designated reporting time frames. • Contacts for SAE reporting can be found in SAE form.

10.3.6. Regulatory Reporting Requirements

SAE Regulatory Reporting

 • Prompt notification by the investigator to the sponsor of a SAE is essential so that legal obligations and ethical responsibilities toward the safety of participants and the safety of a study intervention under clinical investigation are met. • The sponsor has a legal responsibility to notify both the local regulatory authority and other regulatory agencies about the safety of a study intervention under clinical investigation. The sponsor will evaluate the reported SAEs, including confirmation of relatedness and assessment of expectedness. The sponsor has processes for safety reports for identification, recording, and expedited reporting of suspected unexpected serious adverse reactions according to local regulatory requirements. The sponsor will comply with country-specific regulatory requirements relating to safety reporting to the regulatory authority, Institutional Review Boards (IRB)/Independent Ethics Committees (IEC), and investigators. • An investigator who receives an investigator safety report describing a SAE or other specific safety information (for example, summary or listing of SAEs) from the sponsor will review and then file it along with the IB will notify the IRB/IEC, if appropriate according to local requirements.

10.4. Appendix 4: Contraceptive and Barrier Guidance

10.4.1. Definitions

Women of child-bearing potential (WOCBP)

Females are considered WOCBP if they have had at least 1 cycle of menses.

Any amount of spotting or bleeding should be considered menarche.

Women not of child-bearing potential (WNOCBP)

Females are considered WNOCBP if they

- have a congenital anomaly such as Mullerian agenesis
- are infertile due to surgical sterilization, or
- are postmenopausal.

Examples of surgical sterilization include total hysterectomy, bilateral salpingo-oophorectomy, bilateral salpingectomy, or bilateral oophorectomy.

Postmenopausal

The postmenopausal state is defined as ≥ 1 year without a menstrual period confirmed by follicle stimulating hormone test.

10.4.2. Contraception Guidance

Guidance for WOCBP

This outlines the rules for WOCBP to ensure they do not become pregnant during the study.

WOCBP who are completely abstinent as their preferred and usual lifestyle, or in a same-sex relationship as their preferred and usual lifestyle:

Must...	Must not...
agree to either remain abstinent or stay in a same-sex relationship without sexual relationships with males	
 • use periodic abstinence methods 
 ○ calendar ○ ovulation ○ symptothermal, or ○ post-ovulation • declare abstinence just for the duration of a trial, or • use the withdrawal method

WOCBP, who are NOT completely abstinent as their preferred and usual lifestyle, or NOT in a same-sex relationship as their preferred and usual lifestyle, must do the following:

Topic	Condition
Pregnancy testing	Have a negative serum test result at screening (or upon a participant that reaches menarche during the trial and is sexually active) followed by a negative urine result within 24 hours prior to treatment exposure. See the protocol SoA for subsequent pregnancy testing requirements.

Topic	Condition
Contraception	
Agree to use 1 highly effective method of contraception, or a combination of 2 effective methods of contraception.
 
These forms of contraception must be used for the duration of the study.

Examples of different forms of contraception

Methods	Examples
Highly effective contraception (less than 1% failure rate)	
 • female sterilization • combination oral contraceptive pill • progestin-only contraceptive pill (mini-pill) • implanted contraceptives • injectable contraceptives • contraceptive patch (only women <198 pounds or 90 kg) • total abstinence • vasectomy, if only sexual partner • fallopian tube implants, if confirmed by hysterosalpingogram • combined contraceptive vaginal ring, or • intrauterine devices
Effective contraception	
 • male or female condoms with spermicide • diaphragms with spermicide or cervical sponges • barrier method with use of a spermicide 
 ○ condom with spermicide ○ diaphragm with spermicide, or ○ female condom with spermicide. 
NOTE: The barrier method must include use of a spermicide, that is, condom with spermicide, diaphragm with spermicide, and female condom with spermicide, to be considered effective.

Ineffective forms of contraception	
 • spermicide alone • immunocontraceptives • periodic abstinence • fertility awareness (calendar method, temperature method, combination of above 2, cervical mucus, symptothermal) • withdrawal • post coital douche, and • lactational amenorrhea

Guidance for all men

Males may participate in this trial.

No male contraception is required except in compliance with specific local government study requirements.

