Review menarche status with date of menarche (if applicable)	X	X	X	X	X		X		X	X		For participants <18 years of age. If the participant reaches menarche at any time during the trial and is sexually active, pregnancy testing and contraception requirements will apply. See Section 10.4, Appendix 4.

	Period I	Period II									Period III	Comments
	Screening	Baseline	Treatment Period								Post-Treatment Follow-up	
Visit Number	1	2	3	4	5	6	7	8	9	ED	801	
Week Relative to Study Drug Start	≤30 (days)	0	2	4	8	12	16	20	24	-	Approximately 12 weeks post last dose	
Visit Interval Tolerance (Days)		-	±3	±3	±5	±5	±5	±5	±5	-	±7	
Visit Detail						T		T				
Concomitant medications	X	X	X	X	X	X	X	X	X	X	X	
AEs	X	X	X	X	X	X	X	X	X	X	X	Any events that occur after signing the ICF or assent are considered AEs as defined in Section 10.3, Appendix 3. For AESIs, additional data could be collected. See Section 8.3.3.
Physical Evaluation												
Height	X								X			
Weight	X	X					X		X	X		
Vital signs	X	X					X		X	X		Includes pulse rate, blood pressure, respiratory rate, and temperature. Measured after participant has been sitting at least 5 minutes. Use size appropriate blood pressure cuffs.
Physical examination	X								X	X		The physical examination is performed (excludes pelvic and rectal, unless clinically indicated). Full skin examination is required for BSA calculation.
Symptom-directed physical assessment		X	X	X	X		X				X	As indicated based on participant status and standard of care. May be performed by qualified personnel per local regulations.

	Period I	Period II									Period III	Comments
	Screening	Baseline	Treatment Period									
Visit Number	1	2	3	4	5	6	7	8	9	ED	801	
Week Relative to Study Drug Start	≤30 (days)	0	2	4	8	12	16	20	24	-	Approximately 12 weeks post last dose	
Visit Interval Tolerance (Days)		-	±3	±3	±5	±5	±5	±5	±5	-	±7	
Visit Detail						T		T				
Participant Diary (Electronic)												
Diary dispensed	X											Diary includes daily collection of PRO assessments (Pruritus NRS, Sleep-Loss Scale, and Skin Pain NRS); bi-weekly collection of study drug administration information (as applicable). TCS usage will be collected daily beginning at V2. Pruritus NRS and Sleep-Loss Scale should be completed a minimum of 4 of 7 days before baseline.
Review diary for completion of PRO and TCS assessments		X	X	X	X	X	X	X	X	X		For details of these assessments see Section 8.1.
Drug administration diary compliance check					X	X	X	X	X	X		
Diary return									X	X		

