4.4. End of Study Definition

A participant is considered to have completed the study if the participant has completed all periods of the study including the last scheduled procedure shown in the SoA.

The end of the study is defined as the date of the last visit of the last participant in the study or last scheduled procedure shown in the Schedule of Activities (SoA) for the last participant in the study.

5. Study Population

Prospective approval of protocol deviations to recruitment and enrollment criteria, also known as protocol waivers or exemptions, is not permitted.

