5.1. Inclusion Criteria

Participants are eligible to be included in the study only if all of the following criteria apply:

Age

1. Participant must be ≥ 12 years of age inclusive at the time of signing the informed consent/assent.

Type of Participant and Disease Characteristics

2. All participants must have prior treatment with dupilumab meeting one of the following conditions:
 - Participants who stopped dupilumab treatment due to non-response, partial response, loss of efficacy must have been previously treated with dupilumab (at labeled dose level) for at least 4 months.
 - Participants who stopped dupilumab treatment due to intolerance or AEs to the drug may enter the study with no required prior length of dupilumab treatment.
 - Participants who stopped dupilumab treatment due to cost or loss of access to dupilumab (for example, insurance coverage) may enter the study with no required prior length of dupilumab treatment.
3. Participants who have chronic AD (according to American Academy of Dermatology Consensus Criteria; Eichenfield et al. 2014) that has been present for ≥ 1 year before screening visit.
4. Have EASI ≥ 16 at the baseline visit.
5. Have IGA score ≥ 3 (Scale of 0 to 4) at the baseline visit.
6. Have $\geq 10\%$ body surface area (BSA) of AD involvement at the baseline visit
7. Have a history of inadequate response to treatment with topical medications; or determination that topical treatments are otherwise medically inadvisable.

Weight

8. Adolescents body weight must be ≥ 40 kg at baseline.

Sex and Contraceptive/ Barrier Requirements

9. Male and/or female
 - a. Male participants are not required to use any contraception except in compliance with specific local government study requirements.
 - b. Female participants of child-bearing potential: must agree to remain abstinent (refrain from heterosexual intercourse) or use a highly effective contraceptive method during the treatment period and for at least 18 weeks after the last dose of study drug. Women of non-child-bearing potential (non-WOCBP) may participate

without any contraception requirements. For definitions of women of child-bearing potential (WOCBP) and non-WOCBP, see Section 10.4, Appendix 4.

Contraceptive use by participants should be consistent with local regulations regarding the methods of contraception for those participating in clinical studies. For the contraception requirements of this protocol, see Section 10.4, Appendix 4.

Informed Consent

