6.7. Treatment of Overdose

For this study, any dose of lebrikizumab greater than 500 mg (baseline and Week 2) and 250 mg Q2W (Week 4 and beyond) will be considered an overdose.

Sponsor does not recommend specific treatment for an overdose.

In the event of an overdose, the investigator/treating physician should:

- Contact the medical monitor immediately.
- Evaluate the participant to determine, in consultation with the medical monitor, whether study intervention should be interrupted or whether the dose should be reduced.
- Closely monitor the participant for any AE/SAE and laboratory abnormalities until lebrikizumab can no longer be detected systemically (at least 18 weeks).

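### Appendix 4 accepts weaker and shorter contraception than inclusion criterion 9b requires

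*Protocol*

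**What the plan says.** **Criterion 9b (Protocol 5.1).** Female participants of child-bearing potential must be abstinent or "use a highly effective contraceptive method during the treatment period and for at least 18 weeks after the last dose of study drug". Two merely effective methods are not among the options. The same section then refers the reader on: "For the contraception requirements of this protocol, see Section 10.4, Appendix 4".

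**Appendix 4 (Protocol 10.4.2).** Women who are not abstinent, and not in a same-sex relationship, as their usual lifestyle must "Agree to use 1 highly effective method of contraception, or a combination of 2 effective methods of contraception". On duration: "These forms of contraception must be used for the duration of the study". The methods list treats highly effective contraception (failure rate below 1%) and effective contraception (condoms, diaphragms or sponges, and barrier methods with spermicide) as separate classes. The 18-week period appears nowhere in the appendix.

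**Menarche on study.** The Schedule of Activities (Protocol 1.3) states: "If the participant reaches menarche at any time during the trial and is sexually active, pregnancy testing and contraception requirements will apply". The only source it gives is Appendix 4. The definition in 10.4.1 is: "Females are considered WOCBP if they have had at least 1 cycle of menses".

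**Participant-level end of study (Protocol 4.4).** "A participant is considered to have completed the study if the participant has completed all periods of the study", up to the last procedure in the Schedule of Activities. That is Visit 801, about 12 weeks after the last dose.

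**The concern.** The section that sets the contraception rule refers sites for detail to an appendix with a weaker one. The two differ on which methods count and on when contraception may stop. A site working from Appendix 4 alone could accept a woman whom 9b excludes, or stop asking for contraception after Visit 801.

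The exposure is clearest for a girl who has not reached menarche at entry. Under 10.4.1 she is not yet of child-bearing potential, so the 18-week clause of 9b does not apply to her at enrolment. If she reaches menarche during the trial and is sexually active, the text she is directed to lacks the 18-week period and allows the weaker class of methods.

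The overdose section (6.7) gives 18 weeks as the minimum time for lebrikizumab to become undetectable. The earlier stopping point may therefore fall while drug is still present.

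**Working it through.** **Method**

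| | Criterion 9b | Appendix 4, non-abstinent women |
|---|---|---|
| Abstinence | accepted | accepted (listed as highly effective) |
| One highly effective method | accepted | accepted |
| Two effective methods | not accepted | accepted |

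Appendix 4 cannot be read as defining what 9b means by highly effective. It keeps the two classes apart and gives the below-1% failure rate only for the higher one.

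**End date**

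Inputs:
- 18 weeks after the last dose, from criterion 9b.
- Visit 801 at about 12 weeks after the last dose, ±7 days, from the Schema and Schedule of Activities. That is 11 to 13 weeks.
- Last scheduled dose at Week 20 for responders and Week 22 for inadequate responders, from Protocol 6.1.

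Check on the 12-week figure: 30 days of screening (30/7 = 4.3 weeks) + 22 + 12 = 38.3 weeks. This agrees with the planned duration of up to 38 weeks in the Synopsis.

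Shortfall = 18 minus weeks from last dose to Visit 801:
- Nominal: 18 − 12 = 6 weeks.
- With the ±7-day window: 18 − 13 = 5 to 18 − 11 = 7 weeks.
- With the ±14-day window for exceptional circumstances (Appendix 10): 18 − 14 = 4 to 18 − 10 = 8 weeks.

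| | Last dose | Visit 801 | 18-week point |
|---|---|---|---|
| Responders | Week 20 | 20 + 12 = Week 32 | 20 + 18 = Week 38 |
| Inadequate responders | Week 22 | 22 + 12 = Week 34 | 22 + 18 = Week 40 |

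SAP 4.1 also gives Week 34 as an alternative time for Visit 801. For a responder that is 34 − 20 = 14 weeks after the last dose, a nominal shortfall of 18 − 14 = 4 weeks.

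**Which text is out of line**

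The 18-week figure in 9b recurs in the pregnancy-reporting window (8.3.1) and in the overdose section (6.7). On duration, Appendix 4 stands alone. The sponsor would collect pregnancies to 18 weeks, while Appendix 4 on its own would let contraception stop about 6 weeks earlier. The Schedule of Activities has no pregnancy test at Visit 801.

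**The case against.** The strongest reply is that 9b already controls the matter. Every inclusion criterion must be met, waivers are barred (Section 5), and eligibility is confirmed at screening and baseline. A woman relying on two barrier methods fails entry whatever the appendix says. That is right for women of child-bearing potential at enrolment, and it limits the harm. It does not remove the conflict, because Section 5.1 itself tells sites to look in Appendix 4.

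On duration, Appendix 4 does not say that contraception may stop at Visit 801, and a participant can satisfy both texts by following the longer one. Section 4.4 also defines the end of the study as the last participant's last visit. On that reading the gap shrinks or vanishes for early enrollees but remains for the last ones. This makes the 6 weeks conditional. The method conflict is unaffected.

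On menarche, 9b could be read as reaching anyone who becomes of child-bearing potential later. The group is also tiny: about 12 adolescents of both sexes are planned, and possibly none would qualify. Both points are fair. But the Schedule of Activities points such a girl to Appendix 4 only, so the protocol should not leave this to interpretation.

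The 18 weeks in 6.7 is a monitoring instruction after overdose, so it supports the 18-week rule only indirectly. No third section settles which class of method was intended. The case for 9b on method is that it is the binding eligibility criterion and the stricter text.

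**Conclusion.** The concern holds: Appendix 4 is wrong as written, on patient-safety grounds. It accepts a class of methods that 9b does not allow, and it omits the 18-week period.

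If the study means the participant's own participation, contraception ends about 6 weeks early (5 to 7 with the normal visit window). The SAP's Week 34 timing for responders and the exceptional-circumstances window widen that to about 4 to 8 weeks. Participants who enter Continued Access skip Visit 801 and are not counted, because Protocol Addendum 2 was not available.

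The mismatch in the text is certain. How sites would act on it is not, since the consent form was not available either. Sample size, endpoints, estimands and analyses are untouched.

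**What to change.** In Appendix 4, replace the contraception condition with a requirement for one highly effective method throughout treatment and until 18 weeks or more after the last dose. Delete the two-effective-methods option and the sentence tying use to the length of the study. State that the rule also applies to participants who reach menarche on study.

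Two tidy-ups follow. The row for abstinent women and same-sex relationships also has no end date, so stating the period once for both rows would be cleaner. The list of effective methods should be removed or marked as insufficient.

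Leave criterion 9b and the pregnancy row in 8.3.1 as they are. Check that the consent form and Protocol Addendum 2 agree.

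The cost is a wording amendment to one appendix. Any woman relying on two barrier methods would need a highly effective method or abstinence, as 9b already requires.
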